In a recent NIDA funded preclinical study (NIDA Study Report 1812-12132, Sep. 20, 2013), lorcaserin was administered to rodents in combination with cocaine without any significant toxicity. Final results of this study are summarized here and provided in detail in an attached document. In short, at human equivalent doses in rats (i.e., 5 mg/kg, equivalent to 20 mg/day in humans, based on systemic exposures), there were no additive/synergistic effects of PO lorcaserin on IV cocaine-induced mortality or convulsions. However, at 5-fold higher doses (i.e., 25 mg/kg in rats, equivalent to 100 mg/day in humans – substantially beyond what is proposed in this study), there are indications of increased sensitivity to cocaine-induced convulsions due to lorcaserin. The combination of lorcaserin and cocaine has not been studied in humans. We will guard against potential toxicity of cocaine combined with lorcaserin by dosing cocaine using an ascending dose approach, and we have specific stopping criteria in place to stop the cocaine dose escalation if warranted by excessive cardiovascular responses. If in spite of these precautions cocaine toxicity is observed (significant hypertension, tachycardia, symptoms of ischemia or evidence of arrhythmias) we have established treatment protocols in place and a code team will respond if needed. We have never required such assistance in the past. Moreover, additional blood samples will be drawn 4-6 hours on the days of escalating cocaine infusions to measure high-sensitivity troponin I (hsTnI) and N-terminal pro-brain natriuretic peptide (NT-pro-BNP). Although not routinely utilized in clinical practice, these markers will be stored for batch analysis upon completion of the study to detect the presence cardiac strain and/or stress to the myocardium related to cocaine in the absence of overt clinical disease (Gaggin and Januzzi, 2014; Gualandro et al., 2014). This data will be used as a potential biomarker of subclinical effects of cocaine on heart for future clinical trials. The total amount of blood for the entire study will not exceed 550ml in an 8 week period.

Potential Risks Not Due to Study Medication

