The subject would make a series of choices using the PR schedule between ascending value money options (\$5) or cocaine (0 mg or 25 mg/i.v. infusion) using a patient controlled (PCA pump). Choices for money will be verbally indicated to the investigator. Infusions will be made over a 2 min period followed by a 13 min time-out period. Subjects will receive the cash or cocaine doses (0 or 25 mg) immediately after they meet the progressive ratio criteria for each choice, providing vital signs remain within the preset intervals. If the subject chooses all cocaine options in the cocaine choice session and no money, they will receive a maximum of 120 mg cocaine, i.v. Money choices will be given directly to the patient after choice session, but this can only be spent after departing from the CRS. All infusions on this day will be double-blinded and counterbalanced in their presentation among subjects.

Cardiovascular Monitoring During Cocaine Infusions and Cocaine Self-Administration Procedure

Cardiovascular monitoring by continuous measuring heart rate/ECG and blood pressure starting 15 minutes prior to each of the 4 cocaine infusions and continued for at least 60 minutes following each dose. PI/Co-I or their medically qualified designees will be present during all cocaine infusions to monitor and intervene if necessary. For the sessions of cocaine infusions on Day 1, 2, 6, and 10, non-invasive monitoring of cardiac hemodynamics will be performed with the NexFin finger cuff system (Edwards Life Sciences).

Criteria for withholding Cocaine Administration

Cocaine administration will not be initiated if:

- Clinically significant arrhythmias
- Resting pulse > 130 bpm
- QTc increase of greater than 30ms over baseline
- Blood pressure above 165mm Hg systolic and 100mm Hg diastolic.
- Behavioral manifestations of cocaine toxicity (agitation, psychosis, inability to cooperate with study procedures).

If cardiovascular measures have not returned to acceptable levels (heart rate <130 bpm, diastolic pressure <100mmHg, and systolic pressure <165 mmHg, QTc <30ms over baseline), the next session will be delayed by 15 min, after which these measures will be repeated.

Stopping Criteria for Subject Participation

Subject participation will be terminated if any of the following events occur:

The following values do not return to acceptable limits within appropriate time frames (approximately 30 minutes);

- Systolic BP > 180 mm Hg
- Diastolic BP > 120 mm Hg

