- Heart rate > (220 – age x 0.85) bpm
- QTc > 470ms
- Participants must continue to meet other inclusion criteria in order to remain in the protocol

ADVERSE EXPERIENCE REPORTING AND DOCUMENTATION

Adverse Events

Adverse Events (AEs) will be identified through daily interviews with participants and noted at any visit. The data will be entered on the standard VCU IRB AE and SAE forms. Continuous logs of all SAEs and AEs will be maintained. SAEs will be reported to the VCU IRB, the NIDA PO, the DSMB and the US FDA (when appropriate) as described above. In addition to immediate reports where appropriate, there will be annual reports and descriptions in the results section of publications.

Table 4. AE Severity Grading

Severity (Toxicity Grade)	Description
Mild (1)	Transient or mild discomfort; no limitation in activity; no medical intervention or therapy required. The subject may be aware of the sign or symptom but tolerates it reasonably well.
Moderate (2)	Mild to moderate limitation in activity, no or minimal medical intervention/therapy required.
Severe (3)	Marked limitation in activity, medical intervention/therapy required, hospitalizations possible.
Life-threatening (4)	The subject is at risk of death due to the adverse experience as it occurred. This does not refer to an experience that hypothetically might have caused death if it were more severe.

AE Relationship to Study Drug

The relationship of an AE to the study drug will be assessed using the following the guidelines in 5. Table 5. AE Relationship to Study Drug

Relationship to Drug	Comment
Definitely	Previously known toxicity of agent; or an event that follows a reasonable temporal sequence from administration of the drug; that follows a known or expected response pattern to the suspected drug; that is confirmed by stopping or reducing the dosage of the drug; and that is not explained by any other reasonable hypothesis.
Probably	An event that follows a reasonable temporal sequence from administration of the drug; that follows a known or expected response pattern to the suspected drug; that is confirmed by stopping or reducing the dosage of the drug; and that is unlikely to be explained by the known characteristics of the subject's clinical state or by other interventions.

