
[contact]

[contact], [name]

DISCONTINUATION AND REPLACEMENT OF SUBJECTS

Early Discontinuation of Study Drug

A subject may be discontinued from study treatment at any time if the subject, the investigator, or the Sponsor feels that it is not in the subject's best interest to continue. The following is a list of possible reasons for study treatment discontinuation:

Subject withdrawal of consent (or assent)

Subject is not compliant with study procedures

Adverse event that in the opinion of the investigator would be in the best interest of the subject to discontinue study treatment

Protocol violation requiring discontinuation of study treatment

Lost to follow-up

Sponsor request for early termination of study

Positive pregnancy test (females)

Chest discomfort or shortness of breath consistent with ischemia

Systolic BP > 180 mmHg

Diastolic BP > 110 mmHg

Heart rate > Maximum predicted heart rate ($> 220 - \text{age} \times 0.85$) bpm.

If a subject is withdrawn from treatment due to an adverse event, the subject will be followed and treated by the Investigator until the abnormal parameter or symptom has resolved or stabilized.

All subjects who discontinue study treatment should come in for an early discontinuation visit as soon as possible and then should be encouraged to complete all remaining scheduled visits and procedures.

All subjects are free to withdraw from participation at any time, for any reason, specified or unspecified, and without prejudice.

Reasonable attempts will be made by the investigator to provide a reason for subject withdrawals. The reason for the subject's withdrawal from the study will be specified in the subject's source documents Refer to Section 10 for early termination procedures.

Withdrawal of Subjects from the Study

A subject may be withdrawn from the study at any time if the subject, the investigator, or the Sponsor feels that it is not in the subject's best interest to continue.

All subjects are free to withdraw from participation at any time, for any reason, specified or unspecified, and without prejudice.

Reasonable attempts will be made by the investigator to provide a reason for subject withdrawals. The reason for the subject's withdrawal from the study will be specified in the subject's source documents.

Replacement of Subjects

Subjects who withdraw from the study treatment will be replaced.

Subjects who withdraw from the study will be replaced.

Protocol Violations

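### Read as written, the heart-rate stopping limit lies above the predicted maximum heart rate at every eligible age

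*Combined protocol and SAP*

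**What the plan says.** Three sets of cardiovascular limits bear on this point.

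- **Stopping Criteria for Subject Participation.** Termination is mandatory when "The following values do not return to acceptable limits within appropriate time frames (approximately 30 minutes". The listed values are systolic pressure above 180 mm Hg, "Diastolic BP > 120 mm Hg", "Heart rate > (220 – age x 0.85) bpm" and QTc above 470 ms.
- **Early Discontinuation of Study Drug.** This list is introduced by "The following is a list of possible reasons for study treatment discontinuation", so it is discretionary. It gives systolic pressure above 180 mm Hg, "Diastolic BP > 110 mmHg", and the same heart-rate expression, here labelled "Heart rate > Maximum predicted heart rate". No duration is attached.
- **Criteria for withholding Cocaine Administration.** Cocaine is not started with a pulse above 130 bpm, blood pressure above 165/100 mm Hg, a QTc rise above 30 ms over baseline, significant arrhythmia or behavioural toxicity. If a subject's readings "have not returned to acceptable levels (heart rate <130 bpm, diastolic pressure <100mmHg, and systolic pressure <165 mmHg, QTc <30ms over baseline", dosing is put off for 15 minutes and the readings are taken again.

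The section Risks of Lorcaserin Combined with Cocaine relies on such limits as a protection: "we have specific stopping criteria in place to stop the cocaine dose escalation if warranted by excessive cardiovascular responses". It also notes that the combination has not been given to humans before.

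**The concern.** In the termination rule the factor 0.85 sits inside the bracket next to age, so it scales age and not the age-predicted maximum. Subtracting 85% of age from 220 gives a larger number than subtracting all of it. The limit is therefore higher than the predicted maximum, when a safety threshold would be expected to sit below it.

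The second list does not resolve this. It repeats the arithmetic and calls the result the maximum predicted heart rate, which fits neither 220 − 0.85 × age nor 85% of the maximum. Three readings are then possible, and staff applying the rule cannot tell from the text which one governs.

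At stake is a mandatory termination criterion in a first human study of lorcaserin with intravenous cocaine. As written, its heart-rate arm does not act until the rate has passed the predicted maximum, and then only if the rate fails to recover in about 30 minutes.

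Two smaller ambiguities sit in the same rules. The protocol does not say how the two diastolic figures relate, and the termination rule uses the phrase *acceptable limits* without defining it.

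**Working it through.** **Inputs.** The eligible age range is 18 to 59 years (Inclusion Criteria). The heart-rate expression is taken from the two lists as printed. The pre-dose pulse limit is 130 bpm (Criteria for withholding Cocaine Administration). The predicted maximum is taken as 220 − age. The documents do not state that formula separately, so it is an assumption, though the terms of the expression point to it. The plan prints no numerical heart-rate limit by age, so there is no figure to reproduce.

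**Three readings, with a = age in years**

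- As written: 220 − 0.85a
- Label in the discontinuation list: 220 − a
- Probable intent (assumption): 0.85 × (220 − a). This is the only reading in which 0.85 acts as a fraction of the maximum.

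| Age | As written | Predicted maximum | 85% of maximum | Written − maximum | Written − 85% | Written as % of maximum |
|---|---|---|---|---|---|---|
| 18 | 204.7 | 202 | 171.7 | 2.7 | 33.0 | 101.3 |
| 30 | 194.5 | 190 | 161.5 | 4.5 | 33.0 | 102.4 |
| 40 | 186.0 | 180 | 153.0 | 6.0 | 33.0 | 103.3 |
| 50 | 177.5 | 170 | 144.5 | 7.5 | 33.0 | 104.4 |
| 59 | 169.85 | 161 | 136.85 | 8.85 | 33.0 | 105.5 |

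**Excess over the maximum.** (220 − 0.85a) − (220 − a) = 0.15a. This is positive at every age and grows with age, so the written limit is furthest above the predicted maximum in the oldest subjects.

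**Gap to the probable intent.** (220 − 0.85a) − 0.85 × (220 − a) = 220 − 187 = 33 bpm. The age terms cancel, so the gap is the same for everyone.

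**Relation to the pre-dose limit.** The lowest 85% limit is 136.85 bpm, at age 59. That is 136.85 − 130 = 6.85 bpm above the pre-dose limit. A corrected termination threshold therefore stays above the pre-dose limit at every eligible age, and the order of the two rules is preserved.

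**Diastolic limits, side by side.** The termination rule has 120 mm Hg, about 30 minutes without recovery, mandatory. The discontinuation list has 110 mm Hg, no duration, discretionary. The systolic figure is 180 mm Hg in both. The text gives no reason for the 10 mm Hg difference in one and none in the other.

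**Recovery target, by example.** Suppose a subject peaks at 185/125 mm Hg and is at 170/105 mm Hg after 30 minutes. If *acceptable limits* means the 165/100 mm Hg of the delay rule, participation ends. If it means only a return below the triggers of 180/120 mm Hg, it does not.

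**The case against.** The strongest reply is that the protection does not rest on this one expression. The start of any cocaine dose is governed by a separate numeric check, a medically qualified person attends every infusion, and escalation doses are an hour apart. Uncontrolled hypertension or arrhythmia calls for prompt physician evaluation, and stopping rules are on the agenda of the first DSMB meeting. Clinicians may well apply 85% of the predicted maximum whatever the bracket says. All of this stands as a limit on the consequences. None of it corrects the threshold, and the same misplacement in two sections makes a text-extraction fault unlikely.

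Three stronger readings are tempting, and the documents do not support them.

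- *A reader might infer that the next cocaine dose is unregulated, or subject to conflicting diastolic figures.* It is not. One diastolic value (100 mm Hg) and one pulse value (130 bpm) decide whether a dose may start. Neither 110 nor 120 mm Hg enters that decision.
- *A reader might infer that 110 and 120 mm Hg contradict each other.* They need not. A lower discretionary limit beneath a higher mandatory one is a coherent two-tier arrangement. What is missing is a sentence saying that this is what was meant.
- *A reader might infer that the promise of escalation-stopping criteria requires a rule triggered by the peak response to the preceding dose.* The pre-dose check, the termination rule and the discretionary list can together be those criteria. A peak-response rule would be a new clinical choice with a cost. It would remove 40 mg observations selectively in large responders, and heart rate and blood pressure at 40 mg are a primary outcome. Each such dose withheld on lorcaserin is 1 of 12 subjects × 2 sessions = 24 planned, or 4.2%. The documents do not decide that trade-off.

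On *acceptable limits*, the preceding section defines acceptable levels in its last sentence, and carrying that forward is the natural reading. The remedy is a short cross-reference.

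**Conclusion.** The point holds as an error in a safety threshold. Read literally, the heart-rate limit for mandatory termination and for discretionary discontinuation is above 220 − age for every eligible subject, at 101.3% to 105.5% of it. It is 33 bpm above the reading that was probably meant.

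The effect is confined to the termination and discontinuation criteria. It does not change when a cocaine dose may be started.

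Two assumptions carry the conclusion: that the predicted maximum is 220 − age, and that 85% of it was intended. The first fixes the size of the excess over the maximum, and the second fixes the 33 bpm. The literal value of the printed expression depends on neither. The documents give no rate of sustained tachycardia after cocaine, so the number of subjects affected cannot be stated.

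The diastolic and recovery-target points are clarifications, not errors.

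**What to change.** In both Stopping Criteria for Subject Participation and Early Discontinuation of Study Drug, write the limit as 0.85 × (220 − age) bpm, after the sponsor's clinicians confirm that this is what they intend. In the second list, drop the maximum-heart-rate label or reword it as 85% of the predicted maximum. The confirmation matters most for older subjects, where the corrected limit comes within 6.85 bpm of the pre-dose pulse limit.

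Add two clarifications at the same time:

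- State how the diastolic limits relate: 110 mm Hg as a discretionary reason to discontinue with no duration, and 120 mm Hg as mandatory termination after about 30 minutes without recovery.
- State that *acceptable limits* in the termination rule means the levels in the delay rule: heart rate below 130 bpm, blood pressure below 165/100 mm Hg and QTc less than 30 ms over baseline.

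The change is to protocol wording and uses monitoring already planned. Its cost is that somewhat more subjects may be terminated for sustained tachycardia. The documents allow no estimate of how many.

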RATIONALE	The overall goal of this project is to develop initial human data on effects of novel compounds on safety (interactions with cocaine) and efficacy (subjective response to cocaine and self administration data) in non-treatment seeking cocaine use disorder subjects. The compound to be studied will be the 5-HT ₂ CR agonist lorcaserin. Lorcaserin and other 5-HT ₂ CR agonists have been shown to reduce cocaine self-administration and cue reactivity in rodents (Cunningham et al., 2011; Manvich et al., 2012). In addition there is human safety data in non-cocaine using subjects for lorcaserin as it is currently FDA approved for obesity, and safety data from a cocaine interaction study in rodents (included below), but there is no human cocaine interaction/PK data and no PD data to support potential dosages for phase II clinical trials.
STUDY DESIGN	This is a randomized, double-blind, placebo-controlled phase 1b/2a study.
PRIMARY OBJECTIVE	1. Assess interaction between lorcaserin and cocaine in healthy cocaine using subjects. 2. Assess effects of lorcaserin on cocaine self-administration in healthy cocaine using subjects. 3. Assess effect of lorcaserin on subjective response to cocaine in healthy cocaine using subjects. 4. Assess effect of lorcaserin on cocaine PK in healthy cocaine using subjects.
SECONDARY OBJECTIVES	Assess effect of lorcaserin on response inhibition in healthy cocaine using subjects.
NUMBER OF SUBJECTS	18
SUBJECT SELECTION CRITERIA	Inclusion Criteria: In order to participate in this study, subjects must: 1. Males and females between 18 and 59 years-of-age. 2. Understand the study procedures and provide written informed consent. 3. Meet current DSM-5 criteria for cocaine use disorder, at least moderate severity, and current DSM-IV diagnosis of cocaine dependence, but are not seeking treatment. 4. Currently using cocaine by smoking or intravenous route of administration as determined by self-report and have a positive urine

- drug screen for cocaine during screening.
5. Have vital signs as follows: resting pulse below 95 bpm, blood pressures below 140 mm Hg systolic and 90 mm Hg diastolic.
 6. Have no clinically significant abnormalities in the judgment of the study physician in hematology and chemistry laboratory tests including liver function tests.
 7. Have sinus rhythm with normal conduction (including QTcF less than 440 ms) by ECG.

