Possibly	An event that follows a reasonable temporal sequence from administration of the drug; that follows a known or expected response pattern to that suspected drug; but that could readily have been produced by a number of other factors.
Unrelated	An event that can be determined with certainty to have no relationship to the study drug.

Serious Adverse Experiences (SAE)

An SAE is defined as any AE occurring at any dose that results in any of the following outcomes:

- death
- a life-threatening adverse experience
- inpatient hospitalization or prolongation of existing hospitalization
- a persistent or significant disability/incapacity
- a congenital anomaly/birth defect

Other important medical events may also be considered an SAE when, based on appropriate medical judgment, they jeopardize the subject or require intervention to prevent one of the outcomes listed.

Serious Adverse Experience Reporting

All adverse events (AEs) occurring during the course of the study will be collected, documented, and reported to the PI. The occurrence of AEs will be assessed at baseline and each clinic visit during the treatment phase of the study.

AE's deemed to be serious (SAEs), as defined by the FDA, will be systematically evaluated at each clinic visit. Any SAE, whether or not related to study, will be reported to the VCU IRB, the NIDA Program Officer ([name], and the FDA (when appropriate) within 24-48 hours. A full written report to all institutions will follow as soon as possible but in no more than three days. The written report will be in the format required by the local IRB and will contain information regarding the date of the SAE, description of the SAE, severity rating (Grade 1 to 4), assessment of cause, whether the SAE indicates an increased risk for current or future subjects, and whether changes to the informed consent form will be necessary.

In cases of early termination from the study due to SAE, the participant will have appropriate follow-up medical monitoring. Monitoring will continue until the problem has resolved or stabilized with no further change expected, is clearly unrelated to study medication, or results in death. Outcome of SAEs will be periodically reported to NIDA. A summary of the SAEs that occurred during the previous year will be included in the annual progress report to NIDA.

Medical Monitoring

Dr. [name] should be contacted directly at these numbers to report medical concerns or questions regarding safety.

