Adverse event rates will be coded by body system and MedDra classification term. Adverse events will be tabulated by treatment group and will include the number of patients for whom the event occurred, the rate of occurrence, and the severity and relationship to study drug.

Interim Analysis

When approximately 50% of patients have completed the study, an interim analysis for safety will be conducted by the DSMB. Serious adverse events will be monitored by the committee on an ongoing basis throughout the study.

Sample Size and Randomization

This project requires a final sample size of 18 subjects (Six subjects assigned to Group A (placebo) and 12 subjects assigned to Group B (active lorcaserin)). This sample size for effect of lorcaserin on cocaine self-administration was based on previous research showing effects of medication on human cocaine self-administration (Hart et al, 2008). In an effort to increase the power of the study, a Bayesian approach will also be utilized that incorporates information from previous studies. This approach will use a Bayesian hierarchical model with subject at the lowest level of the hierarchy and treatment group at the second level. This model is analogous to the repeated measures ANOVA except that prior information will be introduced. Since many similar studies have been conducted with cocaine users and the same outcome measures we will assign an

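### The causality table (Table 5) mixes expectedness with causality, so a plausibly timed but qualitatively unexpected event fits none of its four rows

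*Combined protocol and SAP*

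**What the plan says.** Table 5 has four rows.

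- *Definitely* can be reached in two ways. The row begins "Previously known toxicity of agent; or an event that follows a reasonable temporal sequence from administration of the drug". The second way adds conditions: "that follows a known or expected response pattern to the suspected drug; that is confirmed by stopping or reducing the dosage of the drug", and no other reasonable explanation.
- *Probably* repeats the timing, pattern and dechallenge conditions, with a softer test of alternative causes.
- *Possibly* needs plausible timing and an event "that follows a known or expected response pattern to that suspected drug; but that could readily have been produced" by other factors.
- *Unrelated* is "An event that can be determined with certainty to have no relationship to the study drug".

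There is no row for unlikely or not assessable.

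The first primary objective in the Protocol Synopsis is "Assess interaction between lorcaserin and cocaine in healthy cocaine using subjects". Risks of Lorcaserin Combined with Cocaine states: "The combination of lorcaserin and cocaine has not been studied in humans". Adverse events are among the primary outcome measures (Dosage/Dosage Regimen, Outcome Measures). The last paragraph of Analysis of Secondary Endpoints tabulates them by treatment group, including "the severity and relationship to study drug".

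The term study drug is not used consistently. The Study Drug Dosage line gives lorcaserin only, while Dispensing covers both cocaine and lorcaserin under that term.

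**The concern.** Whether an event was expected and whether a drug caused it are separate questions. Table 5 answers the second partly through the first. The result is least useful for the event that a first-in-human combination study should be able to record: one with the right timing and no good alternative explanation, but of a kind not seen before.

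The literal *or* in the top row errs in the other direction. A common complaint on lorcaserin's list of known effects can be rated at the highest level without looking at timing, dechallenge or other causes.

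Because one rating covers an unspecified drug, even a correctly rated event does not show whether lorcaserin, cocaine or the two together is held responsible. At stake is the usefulness of the relationship tabulation and of the cause assessment in individual cases.

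**Working it through.** The plan gives no figure to reproduce. The check sets types of event against the rows of Table 5.

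| Event | Definitely | Probably | Possibly | Unrelated |
|---|---|---|---|---|
| A. New kind of event, good timing, positive dechallenge, no other cause | fails (not a known toxicity; no known pattern) | fails (pattern) | fails (pattern; no other factors) | fails (not certain) |
| B. New kind of event, good timing, other factors could explain it | fails | fails | fails (pattern) | fails (not certain) |
| C. Exaggerated heart rate or blood pressure rise after cocaine, on lorcaserin | depends on the drug rated | depends on dechallenge | open | fails (not certain) |
| D. Headache after a blinded capsule | met by the literal first clause | depends on dechallenge | open | fails (not certain) |

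**Events A and B** meet 0 of 4 rows. In all three related rows the condition that excludes them is the pattern condition; for *Possibly* it reads "that follows a known or expected response pattern to that suspected drug".

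**Event C** can be rated. Risks of Lorcaserin Combined with Cocaine foresees cardiovascular toxicity and reports a convulsion signal in rats at five times the equivalent dose. Risks of Lorcaserin Administration mentions a blood pressure effect of lorcaserin. The pattern condition is met, and when lorcaserin is the drug rated, the cocaine infusion is itself another factor, so *Possibly* is open. If cocaine counts as study drug, the same event is a known toxicity and, read literally, *Definitely* in both arms. The rating thus depends on a definition that the table does not give.

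**Event D** shows why known toxicity should not be enough. Risks of Lorcaserin Administration gives incidences from the obesity trials. The ratio placebo / lorcaserin is:

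- headache 10.1/16.8 = 60%
- nausea 5.3/8.3 = 64%
- fatigue 3.6/7.2 = 50%
- dizziness 3.8/8.5 = 45%
- dry mouth 2.3/5.3 = 43%

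If those rates carried over, 12 × 0.168 = 2.0 of 12 lorcaserin subjects would have headache, against 12 × 0.101 = 1.2 expected at the placebo rate. The rates come from another population, so they illustrate the size and do not predict it.

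**Does the comparison by arm make case-level ratings unnecessary?** With 12 and 6 subjects, an event seen in 3 of 12 and 0 of 6 gives a one-sided Fisher p of C(12,3)/C(18,3) = 220/816 = 0.27. The arm comparison stands, but at this size it says little about a rare new event, so the judgement on the single case carries weight.

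**Would removing the pattern condition from *Possibly* alone be enough?** No. Event A would still fail *Possibly*, because that row also requires that other factors could readily explain the event, and it would still fail the two higher rows on pattern.

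**The case against.** The strongest reply is that little depends on the table. The interaction is tested by repeated measures ANOVA on heart rate and blood pressure, and adverse events are summarised by cohort (Analysis of Primary Endpoint). SAEs are reported regardless of relationship, with their own assessment of cause and of added risk (Serious Adverse Experience Reporting). The numeric limits for stopping participation or treatment do not cite the rating. All of this stands, and it limits the severity.

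Three stronger readings are tempting and are not supported.

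- A reader might infer that the interaction effects the trial looks for cannot be classified at all. The effects it measures are changes in heart rate, blood pressure and ECG, which are foreseen and can be rated at least *Possibly*. Only a qualitatively new event lacks a row.
- A reader might infer that every headache or nausea will be rated *Definitely*, even before lorcaserin or on placebo. The text introduces the table as guidelines, and a common headache with plausible timing also meets *Possibly*. The punctuation also allows a reading in which the later conditions apply to known toxicities. On Days 1-2 placebo is single-blind, so staff know that no lorcaserin has been given. From Day 3 the blind means that any over-attribution can occur in both arms.
- A reader might infer that attribution to cocaine is never recorded. The AE forms are not in the document, and Table 5 speaks of the suspected drug. What is shown is an ambiguity, not an omission.

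None of this gives events A and B a row.

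**Conclusion.** The point holds in this limited form. A plausibly timed, qualitatively unexpected event meets none of the four rows as written. On the literal *or*, known toxicity alone is enough for *Definitely*; that part rests on one of two possible readings of the row. The drug being rated is not defined.

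The consequences reach the descriptive tabulation by relationship and the judgement of cause in single cases, including the cause assessment in an SAE report if staff use Table 5 for it. No primary comparison, arm summary or SAE reporting duty changes. Severity is minor to moderate: worth correcting because the combination is new in humans and the correction is cheap, but not a condition for starting.

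**What to change.** In Table 5:

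1. Delete the known-toxicity clause that opens *Definitely*.
2. Remove the pattern condition from *Definitely*, *Probably* and *Possibly*, or keep it as supporting evidence only, so that timing, dechallenge and alternative causes decide the rating.
3. Word *Possibly* so that it takes any plausibly timed event that does not meet a higher row, whether or not another cause is evident. An added row for unlikely or not assessable would close the remaining gap below *Possibly*.
4. Record expectedness as a separate item.
5. Define study drug for this purpose. Record and tabulate relationship separately for lorcaserin, for cocaine and for their combination, by arm.

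The cost is wording in one table and a few extra fields per adverse event on the CRF and AE form. If the institution's standard AE form cannot be altered, the fields can go on the study CRF, where relationship is already recorded. Visits, sample size and the primary analyses do not change.
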